## 7.9 Criteria for Removal from Study

Participants will be removed from study when any of the criteria listed in Section 7.10 applies. All patients who initiate protocol treatment will be included in the safety analysis, and all patients who initiate protocol treatment and receive at least 8 weeks of treatment will be included in overall evaluation of response. All reasons for discontinuation of therapy should be documented clearly in the medical record.

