## 7.10 Discontinuation of Treatment

The reasons for discontinuation or protocol treatment include:

- Evidence of disease progression during treatment at the discretion of the treating investigator
- Non-compliance with the study protocol, including, but not limited to not attending the majority of scheduled visits. The Protocol Chair will determine when non-compliance should lead to removal from study. Note: These patients will still be included in the overall evaluation of safety and response
- Unacceptable major toxicity. Note: These patients will still be included in the overall evaluation of safety and response

- Intercurrent illness or condition that would, in the judgment of the treating investigator, affect assessment of clinical status to a significant degree or require discontinuation of study treatment
- At subject's own request. Note: The reason for discontinuation from the study must be documented. These patients will be included in the overall evaluation of safety and response if any protocol therapy was administered prior to withdrawal
- Study is closed for any reason (e.g. new information shows that the patient's welfare would be at risk if she continued study treatment)
- General or specific changes in the participant's condition render the participant unacceptable for further treatment in the opinion of the treating investigator
- Patients that require a dose delay of > 28 days. If the delay is due to a cause unrelated to study participation, the patient will have the opportunity to continue study if beyond the first 8 weeks of treatment, if clinical benefit is seen, and if deemed eligible to do so by the Protocol Chair of the study
- If the patient requires dose reduction below dose level -1, the patient should be discontinued from the study unless deemed to have clinical benefit that would outweigh the risk. A discussion with the Protocol Chair should be carried out prior to final decision on discontinuation

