## 12. MEASUREMENT OF EFFECT

For the purposes of this study, patients should be re-evaluated for response after every 2 cycles. Response and progression will be evaluated in this study using the international criteria proposed by the revised Response Evaluation Criteria in Solid Tumors (RECIST) Committee (version 1.1). Changes in only the largest diameter (unidimensional measurement) of the tumor lesions are used in the RECIST criteria.

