### 12.1 Definitions

Evaluable for toxicity: All patients will be evaluable for toxicity from the time of their first administration of study treatment drugs.

Evaluable for objective response: Only those patients who have measurable disease present at baseline, have received at least one cycle of therapy, and have had their disease re-evaluated will be considered evaluable for response. These patients will have their response classified according to the definitions stated below.

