### 17.3 Reporting and Exclusions

All patients included in the study must be assessed for safety, tolerability, and response to treatment, even if there are major protocol treatment deviations or if they are ineligible. Each patient will be assigned one of the following categories: 1) complete response, 2) partial response, 3) stable disease, 4) progressive disease, 5) early death from malignant disease, 6) early death from toxicity, 7) early death because of other cause, or 9) unknown (not assessable, insufficient data). All of the patients who met the eligibility criteria (with the possible exception of those who received no study medication) should be included in the main analysis of the response rate. Patients in response categories 4-9 should be considered to have a treatment failure (disease progression). Thus, an incorrect treatment schedule or drug administration does not result in exclusion from the analysis of the response and clinical benefit rate.

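### The eight-week rule in section 7.9 contradicts sections 7.10 and 17.3 on who enters the response analysis, and CBR has no explicit denominator

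*Combined protocol and SAP*

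**What the plan says.** Six places in the combined protocol and SAP bear on the response population.

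- **Section 7.9:** "all patients who initiate protocol treatment and receive at least 8 weeks of treatment will be included in overall evaluation of response". The same sentence puts everyone who starts treatment in the safety analysis.
- **Section 7.10:** for toxicity, "Unacceptable major toxicity. Note: These patients will still be included in the overall evaluation of safety and response". Non-compliance carries the same note. For withdrawal at the patient's own request, "These patients will be included in the overall evaluation of safety and response if any protocol therapy was administered prior to withdrawal". None of these notes sets a minimum duration.
- **Section 7.11:** a patient who leaves in cycle 1 for reasons clearly unrelated to study treatment, and/or receives under 75% of the intended cycle 1 dose, is treated as not evaluable and may be replaced. The analysis concerned is not named.
- **Section 12.1:** evaluable for objective response are "Only those patients who have measurable disease present at baseline, have received at least one cycle of therapy, and have had their disease re-evaluated". Section 4.1.6 admits patients with non-measurable disease.
- **Section 17.2.2:** ORR and CBR are to be reported as percentages with 95% confidence intervals. No denominator is given.
- **Section 17.3:** the rule covers every eligible patient, "with the possible exception of those who received no study medication) should be included in the main analysis of the response rate". Then: "Patients in response categories 4-9 should be considered to have a treatment failure (disease progression". Those categories cover progression, the early deaths and unknown outcome. CBR appears once, where an incorrect schedule or administration "does not result in exclusion from the analysis of the response and clinical benefit rate".

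**The concern.** Section 7.9 does not use the word only. But its sentence already places every treated patient in the safety analysis, so the eight-week condition has a purpose only if it keeps some of them out of the response analysis. Read that way, it contradicts 7.10 on the next lines and 17.3 in the statistics chapter.

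The patients it removes are not a random subset. Section 12 says that "patients should be re-evaluated for response after every 2 cycles", and two 28-day cycles are 8 weeks. A patient who stops everything before then has usually had no scheduled chance to show a response. Removing such patients takes failures out of the denominator and leaves the numerator almost untouched.

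ORR and CBR, with PFS, are the trial's measures of anti-tumor effect, and section 3.5 foresees a randomized phase II trial. If the denominator is settled only after the data are seen, the more favorable figure can be chosen.

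**Working it through.** **Reading the rules side by side.** Each patient below is eligible and treated.

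| Patient | 7.9 | 7.10 | 7.11 | 12.1 | 17.3 |
|---|---|---|---|---|---|
| A. Stops all drugs for toxicity in week 3, no later scan | out | in | does not apply | not evaluable | in, failure |
| B. Withdraws in week 3 at own request, reason unrelated to treatment, no later scan | out | in | not evaluable, analysis not named | not evaluable | in, failure |
| C. Measurable disease, progresses on a scan 5 days early (56 - 5 = 51 days), then stops all drugs | out | no note | does not apply | evaluable | in, failure |
| D. Non-measurable disease only, treated beyond 8 weeks | in | not relevant | does not apply | not evaluable | in |

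The 5-day window in row C is in note 3 to the study calendar. Rows A and B show 7.9 and 7.10 in direct conflict, and rows A to C show 7.9 in conflict with 17.3. A patient who permanently stops only erdafitinib or only palbociclib may continue the other drugs under section 8.5 and can stay in the 7.9 set. So what matters is stopping all treatment.

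**Size of the shift from 7.9.** The documents give no expected ORR, CBR or early-stopping rate, so there is no stated figure to reproduce and every input here is assumed. Let N be the eligible treated patients, R those with the outcome, r those among R who stopped all treatment before 8 weeks, and d the share stopping all treatment before 8 weeks.

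- Rate under 17.3: R/N.
- Rate under 7.9: (R - r)/[N(1-d)].
- Ratio: (1 - r/R)/(1-d), which exceeds 1 whenever r/R is below d.
- With r = 0 the ratio is 1/(1-d): 1/0.90 = 1.11 for d = 10%, and 1/0.80 = 1.25 for d = 20%. It does not depend on N.

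Illustration with N = 30 (planned enrollment is 26 to 35), 6 responders, 12 with clinical benefit, r = 0:

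| | 17.3 | 7.9, d = 10% | 7.9, d = 20% |
|---|---|---|---|
| ORR | 6/30 = 20.0% | 6/27 = 22.2% | 6/24 = 25.0% |
| CBR | 12/30 = 40.0% | 12/27 = 44.4% | 12/24 = 50.0% |

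ORR rises by 2.2 to 5.0 points and CBR by 4.4 to 10.0 points. At the ends of the planned range, with counts rounded to whole patients:

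- N = 26, 6 responders: 6/26 = 23.1% becomes 6/23 = 26.1% or 6/21 = 28.6%.
- N = 35, 8 responders: 8/35 = 22.9% becomes 8/32 = 25.0% or 8/28 = 28.6%.

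For comparison, the Wilson 95% interval for 6/30 is 9.5% to 37.3%.

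**Section 12.1.** No figure is put on this. Its condition is one cycle (4 weeks) plus a re-evaluation, so its losses need not equal d, and nothing in the documents gives them.

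**The case against.** The strongest reply is that the plan already has a governing rule. Section 17.3 directly follows 17.2.2, calls its analysis of the response rate the main one, and says how failures are counted. For ORR that stands. A reader might infer from the silence of 17.2.2 that ORR has no denominator anywhere, and the documents do not support that. But no text makes the 7.9 set supportive, and 7.10 uses the same term as 7.9 for the evaluation, so the contradiction remains.

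A reader might also infer that 12.1 prescribes a rival ORR denominator. That goes too far. Section 12.1 says whose response will be classified; a patient it leaves out can be placed in the unknown category of 17.3 and counted as a failure. Sections 7.8 and 12.3.5 and note 18 to the study calendar also provide for follow-up to progression after stopping, which may supply a re-evaluation for some early stoppers. The restriction to measurable disease is legitimate in itself. What remains is that the opening word of the 12.1 rule invites a narrower denominator.

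It could also be said that 17.3 settles CBR. It does so only in part: CBR is named just to bar exclusions for incorrect schedule or administration.

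Finally, the endpoints are secondary and descriptive, and the shift lies inside the confidence interval. Both are true. They limit the importance of the point, but a shift of known direction is not sampling noise, and removing it costs a few sentences.

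**Conclusion.** The contradiction between 7.9 on one side and 7.10 and 17.3 on the other is real. Using 7.9 would raise ORR and CBR by a factor of about 1.11 to 1.25. This assumes that 10-20% stop all treatment before 8 weeks and that none of them responds or benefits. If some do, the factor is smaller, and the shift stays upward as long as early stoppers do worse than the rest. Section 12.1 is ambiguous rather than contradictory, 7.11 does not say which analysis it concerns, and CBR lacks an explicit population.

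The effect is confined to descriptive estimates. No test, sample size or power rests on ORR or CBR. DLT, MTD and the recommended phase II dose, which sections 17.2.1 and 7.5 base on toxicity and tolerability, are unaffected. A reader might infer that dose selection is at risk, and the documents give no support for that.

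**What to change.** Let the main analysis in 17.3 govern, and bring the other sections into line.

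1. **7.9:** delete the eight-week condition, or refer to 17.3 for the response population.
2. **12.1:** state that this set governs response classification or a supportive analysis and does not define the main ORR denominator.
3. **17.2.2:** state that both ORR and CBR use the 17.3 main-analysis population, with patients who have no post-baseline assessment counted as non-responders and as without clinical benefit.
4. **7.11:** state which analysis the non-evaluable label refers to, and that treated eligible patients who are replaced stay in the 17.3 response denominator.

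Section 7.10 needs no change. An ORR in patients with measurable disease at baseline, under the same failure rule, is optional.

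The cost is wording only, with no added patients or data. The downside is that reported ORR and CBR will be somewhat lower than under 7.9: in the illustration, 20.0% instead of 22.2-25.0% for ORR and 40.0% instead of 44.4-50.0% for CBR.

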## 7.10 Discontinuation of Treatment

The reasons for discontinuation or protocol treatment include:

- Evidence of disease progression during treatment at the discretion of the treating investigator
- Non-compliance with the study protocol, including, but not limited to not attending the majority of scheduled visits. The Protocol Chair will determine when non-compliance should lead to removal from study. Note: These patients will still be included in the overall evaluation of safety and response
- Unacceptable major toxicity. Note: These patients will still be included in the overall evaluation of safety and response

- Intercurrent illness or condition that would, in the judgment of the treating investigator, affect assessment of clinical status to a significant degree or require discontinuation of study treatment
- At subject's own request. Note: The reason for discontinuation from the study must be documented. These patients will be included in the overall evaluation of safety and response if any protocol therapy was administered prior to withdrawal
- Study is closed for any reason (e.g. new information shows that the patient's welfare would be at risk if she continued study treatment)
- General or specific changes in the participant's condition render the participant unacceptable for further treatment in the opinion of the treating investigator
- Patients that require a dose delay of > 28 days. If the delay is due to a cause unrelated to study participation, the patient will have the opportunity to continue study if beyond the first 8 weeks of treatment, if clinical benefit is seen, and if deemed eligible to do so by the Protocol Chair of the study
- If the patient requires dose reduction below dose level -1, the patient should be discontinued from the study unless deemed to have clinical benefit that would outweigh the risk. A discussion with the Protocol Chair should be carried out prior to final decision on discontinuation

### **7.11 Replacement of Patients Who Discontinue Early**

In general, the study intends that patients would be treated until disease progression or intolerable toxicity. During the phase Ib dose escalation period and phase II portion of the study, if a patient discontinues study treatment for reasons clearly not related to study treatment, after completing fewer than one planned cycle of study, and/or receiving <75% of the total intended dose of study drugs over the first cycle of treatment, then that patient will be considered not evaluable and may be replaced with a new patient.

### **7.12 Withdrawal from Study**

The reasons for withdrawal from the study include:

- Subject withdraws consent for follow-up
- Subject is lost to follow-up
- Study is terminated for any reason

## **8. EXPECTED TOXICITIES AND DOSING DELAYS/DOSE MODIFICATIONS**

### **8.1 Erdafitinib**

#### **8.1.1 Most common anticipated toxicities (refer to IB for further details)**

- Hyperphosphatemia
- Decrease in appetite
- Dry mouth
- Nail and skin toxicities
- Palmar-plantar erythrodysesthesia
- Mucositis (mouth sores)
- Dysgeusia
- Constipation
- Diarrhea
- Fatigue/asthenia

- Reversible retinal pigment epithelial detachment (RPED or central serous retinopathy [CSR])
- Nausea

#### 8.1.2 Adverse events of special interest

Central serous retinopathy was reported in 52 subjects (10.4%) across 5 studies at all doses and 32 subjects (14.4%) at the 8 or 9 mg dose. Events of CSR included preferred terms of , retinal detachment (18 subjects), chorioretinopathy (15 subjects), detachment of retinal pigment epithelium (11 subjects) and retinal edema (5 subjects). Most events were Grade 1 or Grade 2 (data cut-off 4 June 2019, IB v. 8). Drug-induced CSRs are generally reversible.

#### 8.1.3 Adverse events of clinical importance

##### 8.1.3.1 Skin, mucosal, and nail changes

Skin, mucosal and nail toxicities are commonly reported in erdafitinib studies. Nail toxicity were reported in 44.3% of subjects at all doses (56.8% at the 8 or 9 mg dose) and skin toxicity in 42.3% of subjects (45.9% at the 8 or 9 mg dose) from 5 pooled studies (data cut-off June 2019, IB v 8). While frequent and known to be associated with FGFR inhibitors, these toxicities respond well to medical management and did not necessitate permanent changes in treatment.

##### ***General recommendations to avoid skin toxicities:***

- Avoid unnecessary exposure to sunlight and excessive use of soap.
- Avoid bathing in excess; use tepid rather than hot water.
- Use moisturizers regularly; apply thick, alcohol-free and oil-in-water based emollient cream on exposed and dry areas of the body.
- Avoid perfumed products, bubble bath, perfumed soaps, and take breaks from shaving.
- Use broad-spectrum sunscreen with a skin protection factor (SPF)  $\geq 15$ .
- Wear cotton clothes next to skin rather than wool, synthetic fibers, or rough clothing.
- Use occlusive alcohol-free emollient creams (jar or tub) for treatment of mild/moderate xerosis.
- For scaly areas, use exfoliants (ammonium lactate 12% or lactic acid cream 12%).

##### ***General recommendations to prevent mucositis:***

- Good oral hygiene
- Use a soft toothbrush
- Avoidance of spicy, acidic, hard, and hot food and beverages
- Use of mild-flavored toothpastes
- Use of saline-peroxide or salt and soda mouthwashes 3 or 4 times per day
- Water soluble lubrication agents like artificial saliva (for xerostomia or dry mouth)

##### ***General recommendations to prevent nail toxicities:***

- Good hygienic practices, keep fingers and toes clean.
- Keep nails trimmed
- Use gloves for housecleaning and gardening to minimize damage and prevent infection
- Nail polish and imitation fingernails should not be worn until the nails have grown out and returned to normal
- Wearing comfortable shoes (wide sized shoes with room for the toes)
- Trimming nails but avoiding aggressive manicuring

### 8.1.3.2 Hyperphosphatemia

Hyperphosphatemia, an expected class effect of FGFR inhibitors, was the most frequently reported AE of clinical importance in Study EDI1001 (65.2% of subjects, Table 49 of IB) and in Study BLC2001 (54.3% of subjects, Table 50 of IB). To further understand the occurrence of hyperphosphatemia, an analysis of serum phosphate levels was conducted in Study EDI1001. The average baseline phosphate level for 187 subjects across tumor types was 3.4 mg/dL with a median of 3.4 mg/dL and range of 1.5-5.2 mg/dL. The profile of mean percent change in phosphate levels over time showed phosphate levels peaked between Cycles 1 and 2 of treatment with erdafitinib. Increases in phosphate were dose dependent; at 9 mg daily, the maximum mean phosphate concentration was 7.3 mg/dL on Cycle 1 Day 21. The trend in mean phosphate levels showed a decline in phosphate level changes from baseline over time beginning at approximately Cycle 3 of treatment. Thus maximum phosphate elevations were transient and serum phosphate levels stabilized even with continued exposure to erdafitinib. If use of a phosphate binder is required and sevelamer hydrochloride (Renagel) is not available, use of other phosphate binders (non-calcium containing) based on the local standard is recommended, including Sevelamer carbonate (Renvela) or lanthanum carbonate (Fosrenol).

### 8.1.3.3 Arrhythmias

Arrhythmia is no longer an AE of clinical importance. Due to the preclinical signal, arrhythmias remain were designated as clinically important; however, the potential cardiac liability of erdafitinib has not been observed in clinical studies. A review of the QTcF intervals and the pharmacokinetic/pharmacodynamic relationships for erdafitinib revealed no effects of erdafitinib on cardiac repolarization or other electrocardiographic parameters. Thus the potential cardiac liability of erdafitinib has, to date, not been observed in clinical studies.

### 8.1.3.4 Ocular toxicities

Ocular toxicities such as dry eyes, keratitis and reversible retinal pigment epithelial detachment (RPED or central serous retinopathy [CSR]/ choroidopathy) have been noted with erdafitinib and other FGFR inhibitors. Eye toxicity was reported by 41.1% of subjects in all doses from 5 studies (data cut-off June 2019, IB v8), the most common events ( $\geq 5\%$  overall) were dry eye, lacrimation increased, vision blurred, and conjunctivitis.

Retinal pigment epithelial detachment is the separation of the retinal pigment epithelium (RPE) from the Bruch's membrane due to the presence of sub-RPE fluid, blood, fibrovascular membrane, or drusenoid material and is attributed to the disruption of the ionic pump of the RPE cells or hyperpermeability of the choroidal vasculature. Drug-induced RPED/CSRs are generally reversible.

#### 8.1.3.4.1 Assessment and evaluation plan for new subjects and subjects during study without ocular symptoms

All patients exposed to erdafitinib should have a baseline assessment of visual acuity, tonometry, fundoscopy (examination of both central and peripheral zones should be performed) and Amsler Grid test, and, where available, an optical coherence tomography (OTC) should be performed. The ophthalmological test should be performed once during screening. Additional exams should be performed as clinically necessary based on the findings of the Amsler grid test and clinical assessment.

An Amsler grid test should be performed at the beginning of every new cycle and at the end of treatment, to identify any new abnormalities (observation of wavy, broken or distorted lines or a blurred or missing area of vision).

- If the subject is asymptomatic and the Amsler grid test is negative, patient will continue study medication at current dose and schedule.
- If the subject is asymptomatic and the Amsler grid test is positive (observation of wavy, broken or distorted lines or a blurred or missing area of vision) then the subject should have a full ophthalmological exam as described, within 7 days. If this is not possible then the study drug should be withheld until a full ophthalmological exam is performed.
- If the subject has ocular abnormalities, manage as per the Dose Modification guidelines for ocular toxicity (Section 8.4).

#### 8.1.3.4.2 Assessment and evaluation plan for any subject during study with ocular symptoms

Subjects that have ocular symptoms at any time should be managed as per the "Management Guidelines for Eye Toxicity Associated with Vision Changes".

Additional modification to the type and or frequency of these exams could be made based on emerging data and/or in consultation with regulatory agencies. If and when such changes are made they will be communicated and incorporated into existing protocols.

When central serous retinopathy (CSR)/retinal pigment epithelial detachments (RPED) is suspected then an OCT should be performed. Fluorescein angiography could be considered appropriate in conditions such as suspected retinal vein occlusion (RVO). It is also recommended that color fundus photos or OCT images be obtained and stored in the patient's file for future reference. In patients with suspected retinal pathology such as CSR or RVO a consultation with a retina specialist should be considered.

